13.4 Reporting Protocol Deviations

The Investigator is obligated to follow the protocol without departure from the requirements written in the protocol. If the Investigator deems a deviation from the protocol requirements is necessary for a particular subject, the Sponsor will be notified and consulted prior to the subject's continuation in the study. The Sponsor also has the right to discontinue the subject for protocol violations. The IRB may also have to be contacted if safety to the subject or if the scientific soundness of the study is involved. All protocol deviations must be documented in the CRFs.

13.5 Subject Premature Withdrawal from Study

A subject who is enrolled into the study but does not complete the study will be considered prematurely discontinued.

All subjects have the right to withdraw at any point during the study without prejudice. It will be documented whether or not each subject completed the clinical study. If, for any subject, study treatment or observations were discontinued, the reason(s) will be recorded and the Sponsor should be notified promptly. All efforts must be made to collect data and report records and test results as completely as possible. Reasons for subject withdrawal/discontinuation may constitute one of the following:

- Subject withdrew consent
- Subject chooses to withdraw from study
- Subject is withdrawn due to an AE
- Pregnancy
- Lost to follow-up
- The Investigator determines that it is in the subject's best interest
- Excessive protocol deviations, as determined by the Investigator
- Discontinuation of study by the Sponsor

Important Notes:

1. Subjects may drop out or be withdrawn at their own request. Although subjects do not need to give a reason for requesting withdrawal from the trial, the Investigator should make a reasonable effort to ascertain the reason(s), while fully respecting the subject's rights.
2. Any subjects reporting Serious Adverse Events (SAEs) that have not resolved by their last study visit will be followed to resolution or until 30 days after the subject completes the study.
3. Every attempt should be made to collect follow-up information. The reason for withdrawal from the study (if known) will be recorded in the source documents and on the appropriate page of the CRF.
4. Before a subject is identified as lost-to-follow-up, the site should make all reasonable efforts to contact the subject. These attempts must be documented and should include at a minimum one phone call and one follow-up certified letter.

14. DATA AND SAFETY MONITORING COMMITTEE

In addition to the requirements for adverse event reporting as outlined in Section 11.0, this protocol is also subject to the UC Davis Cancer Center's (UCDCC) Data and Safety Monitoring Plan. The UCDCC is committed to pursuing high-quality patient-oriented clinical research and has established mechanisms to ensure both scientific rigor and patient safety in the conduct of clinical research studies. The UCDCC relies on a multi-tiered committee system that reviews and monitors all cancer clinical trials and ensures the safety of its participants, in compliance with institutional

and federal requirements on adverse event (AE) reporting, verification of data accuracy, and adherence to protocol eligibility requirements, treatment guidelines, and related matters. The Scientific Review Committee (SRC) assumes overall oversight of cancer studies, with assistance and input from two independent, but interacting, committees: the Quality Assurance Committee and the Data and Safety Monitoring Committee. A multi-level review system strengthens the ability of the UCDCC to fulfill its mission in conducting high quality clinical cancer research.

According to the UCDCC Data and Safety Monitoring Plan, any new serious adverse events related to the drugs being used on this trial are reviewed monthly by the UCDCC Data and Safety Monitoring Committee and any applicable changes to the study are recommended to the PI, if necessary.

The UCDCC SRC determines if a UCDCC Data and Safety Monitoring Board (DSMB) is required. If required, the Data and Safety Monitoring Committee will appoint a DSMB. The DSMB is responsible for reviewing study accrual logs, adverse event information and dose escalation meeting minutes (where applicable) to ensure subject safety and compliance with protocol defined guidelines.

Results of the DSMC audit will be communicated to CellSight, IRB and the appropriate regulatory authorities at the time of continuing review, or in an expedited fashion, as needed.

15. ETHICAL CONSIDERATIONS AND ADMINISTRATIVE PROCEDURES

15.1 Ethics and Good Clinical Practice

This study must be carried out in compliance with the protocol and Good Clinical Practice, as described in:

1. ICH Harmonized Tripartite Guidelines for Good Clinical Practice 1996.
2. Directive 91/507/EEC, The Rules Governing Medicinal Products in the European Community.
3. US 21 Code of Federal Regulations dealing with clinical studies (including parts 50 and 56 concerning informed consent and IRB regulations).
4. Declaration of Helsinki, concerning medical research in humans (Recommendations Guiding Physicians in Biomedical Research Involving Human Subjects, Helsinki 1964, amended Tokyo 1975, Venice 1983, Hong Kong 1989, Somerset West 1996).

The investigator agrees, when signing the protocol, to adhere to the instructions and procedures described in it and thereby to adhere to the principles of Good Clinical Practice that it conforms to.

15.2 IND Holder Information

CellSight Technologies is the holder of the IND (IND# 123591). The company is sponsoring this clinical trial and is responsible for the imaging costs incurred in the trial. The radiotracer will be manufactured under the direction of CellSight Technologies at a qualified production site.

15.3 Institutional Review Board/Independent Ethics Committee

Before implementing this study, the protocol, the proposed informed consent form and other information to subjects, must be reviewed by a properly constituted Institutional Review Board Committee (IRB). A signed and dated statement that the protocol and informed consent have been approved by the IRB must be given to Cellsight before study initiation. Any amendments to the protocol, other than administrative ones, must be approved by this committee.

15.4 Informed Consent

The investigator must explain to each subject (or legally authorized representative) the nature of the study, its purpose, the procedures involved, the expected duration, the potential risks and benefits involved and any discomfort it may entail. Each subject must be informed that participation in the study is voluntary and that he/she may withdraw from the study at any time and that withdrawal of consent will not affect his/her subsequent medical treatment or relationship with the treating physician.

This informed consent should be given by means of a standard written statement, written in non-technical language. The subject should read and consider the statement before signing and dating it and should be given a copy of the signed document. If the subject cannot read or sign the documents, oral presentation may be made or signature given by the subject's legally appointed representative, if witnessed by a person not involved in the study, mentioning that the patient could not read or sign the documents. No patient can enter the study before his/her informed consent has been obtained.

The method of obtaining and documenting the informed consent and the contents of the consent will comply with ICH-GCP and all applicable regulatory requirement(s). In accordance with UCD policy an original signed and dated participant Informed Consent document will reside in a secured location within the department of radiology. Copies of the signed and dated Informed Consent document will be provided to the study participant and UCD Health System Information Management for inclusion in the participant's UCD Health System Medical Record.

The informed consent form is considered to be part of the protocol and must be submitted by the investigator with it for IRB/IEC/REB approval.

Women of child bearing potential should be informed that taking the study drug may involve unknown risks to the fetus if pregnancy were to occur during the study and agree that in order to participate in the study they must adhere to the contraception requirement for the duration of the

study. If there is any question that the patient will not reliably comply, they should not be entered in the study.

15.5 Sharing of Results with Subjects

The results of this research will not be shared with subjects. However, results may be shared as described in Section 7.1.1.

15.6 Disclosure and Confidentiality

I understand that if this study involves the use of the UC Davis Health Electronic Health Record (EMR/EPIC) it also contains the clinical data for Marshall Medical Center (MMC). I understand that MMC patient data cannot be accessed for research purposes and that I must take the necessary steps to ensure that MMC data is not accessed, used, or disclosed for UC Davis Health research purposes.

In order to maintain patient privacy, all study reports and communications will identify the patient by initials and the assigned patient number. Data capture records and drug accountability records will be stored in secure cabinets in the department of radiology. Medical records of patients will be maintained in strict confidence according to legal requirements. The patient's confidentiality will be maintained and will not be made publicly available to the extent permitted by the applicable laws and regulations.

Participant confidentiality is strictly held in trust by the participating investigators, their staff, and the sponsor(s) and their agents. This confidentiality is extended to cover testing of biological samples and genetic tests in addition to the clinical information relating to participants. Therefore, the study protocol, documentation, data, and all other information generated will be held in strict confidence. No information concerning the study or the data will be released to any unauthorized third party without prior written approval of the sponsor.

The study monitor, other authorized representatives of the sponsor, representatives of the IRB or pharmaceutical company supplying study product may inspect all documents and records required to be maintained by the investigator, including but not limited to, medical records (office, clinic, or hospital) and pharmacy records for the participants in this study. The clinical study site will permit access to such records.

The study participant's contact information will be securely stored at the clinical site for internal use during the study. At the end of the study, all records will continue to be kept in a secure location for as long a period as dictated by local IRB and Institutional regulations.

Study participant research data, which is for purposes of statistical analysis and scientific reporting, will be stored according to IRB approved specifications, and will be transmitted to the Sponsor. This will not include the participant's contact or identifying information. Rather, individual participants and their research data will be identified by a unique study identification number. The study data entry and study management systems used by clinical sites and by Sponsor research

staff will be secured and password protected. At the end of the study, all study databases will be de-identified and archived as per IRB approved specifications.

15.7 Declaration of Helsinki

The investigator must conduct the trial in accordance with the principles of the Declaration of Helsinki. Copies of the Declaration of Helsinki and amendments will be provided upon request or can be accessed via the website of the World Medical Association at http://www.wma.net/e/policy/17-c_e.html.

15.8 Compensation for Research-Related Injury

If a subject is injured as a result of being in this study, the University of California will provide necessary medical treatment. Depending on the circumstances, the costs of the treatment may be covered by the University or the study sponsor or may be billed to the subject's insurance company just like other medical costs. The University and the study sponsor do not normally provide any other form of compensation for injury.

15.9 Economic Burden to Subjects

All study-related procedures will be paid by the study and not charged to the subject.

17. APPENDICES

Appendix 1: ECOG and Karnofsky Performance Status Scores^{1,2}

ECOG PERFORMANCE STATUS	KARNOFSKY PERFORMANCE STATUS
0—Fully active, able to carry on all pre-disease performance without restriction	100—Normal, no complaints; no evidence of disease 90—Able to carry on normal activity; minor signs or symptoms of disease
1—Restricted in physically strenuous activity but ambulatory and able to carry out work of a light or sedentary nature, e.g., light house work, office work	80—Normal activity with effort, some signs or symptoms of disease 70—Cares for self but unable to carry on normal activity or to do active work
2—Ambulatory and capable of all selfcare but unable to carry out any work activities; up and about more than 50% of waking hours	60—Requires occasional assistance but is able to care for most of personal needs 50—Requires considerable assistance and frequent medical care
3—Capable of only limited selfcare; confined to bed or chair more than 50% of waking hours	40—Disabled; requires special care and assistance 30—Severely disabled; hospitalization is indicated although death not imminent
4—Completely disabled; cannot carry on any selfcare; totally confined to bed or chair	20—Very ill; hospitalization and active supportive care necessary 10—Moribund
5—Dead	0—Dead

2. Zubrod C, et al. Appraisal of methods for the study of chemotherapy in man: Comparative therapeutic trial of nitrogen mustard and thiophosphoramide. Journal of Chronic Diseases; 1960:11:7-33.

Appendix 2: Study Registration and Participant visits

- A. The subject will sign and date the Informed Consent Form (ICF), and Health Insurance Portability and Accountability Act (HIPAA) authorization (according to site's practices) prior to any study-related procedures with the exception of the standard-of-care (SOC) diagnostic/tumor staging CT or MRI that would be accepted for imaging review to assess eligibility of NSCLC subjects, if done within 45 days prior to Visit 2.
- B. Once signed, informed consent has been obtained; patients will be entered on study. To register a patient, the study coordinator must complete the Eligibility Checklist. The study coordinator will register the patient onto the study and assign a unique an Enrollment ID before initiation of the study drug administration.
- C. Pre-study laboratory tests must be completed prior to registration within the time frame specified in the protocol.
- D. A subject failing to meet all protocol requirements may not be registered. If you have any questions regarding eligibility, please contact the coordinating site PI or Study Coordinator
- E. Unscheduled visits may be required in addition to the scheduled visits per the Investigator's discretion. The details of these unscheduled visits with subjects will be recorded in the medical records and on the Case Report Form (CRF).
- F. If a subject misses a visit, the site is to make every effort to have the subject return as soon as possible to make up the visit. Once the subject is seen, he/she is to return to his/her original visit schedule.
- G. A subject who has signed the consent form but does not receive any [¹⁸F]F-AraG infusion is classified as a screen failure. Subject number, demographic information, and reason for screen failure will be collected.
- H. A subject who is classified as a screen failure will be replaced. A subject who does not receive at least one infusion of [¹⁸F]F-AraG and the associated PET/CT scans will also be replaced.

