10.5 Safety Outcome Measures

- Incidence of Treatment-Emergent Adverse Events (AEs).
- Incidence of withdrawals due to AEs.
- Serious Adverse Events (SAEs)

Analyses of safety outcomes will be conducted using the safety population. Adverse events will be coded using MedDRA. Treatment Emergent AE's (TEAE) are defined as events with an onset on or after the first treatment. TEAEs will be summarized by treatment group and by stage of the study, System Organ Class, and preferred term. The following TEAE summaries will be provided:

- TEAEs by severity grade
- TEAEs by relationship to study treatment.

In addition, separate summaries of serious adverse events, and adverse events resulting in discontinuation of study treatment will be presented.

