11.5 Statistical Methods

11.5.1 Subject Disposition

The disposition of all subjects who sign an ICF will be provided. The numbers of subjects screened, enrolled, completed, and discontinued during the study, as well as the reasons for all post-

enrollment discontinuations will be summarized for healthy and NSCLC subjects respectively. Disposition and reason for study discontinuation will also be provided as a by-subject listing.

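### Does a registered subject who stops before infusion need a new rule, given that Appendix 2 G and section 13.5 label that subject differently?

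*Combined protocol and SAP*

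**What the plan says.** Four places bear on how a subject who never receives tracer is counted.

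- **Appendix 2, items B, D, G and H.** Under B the coordinator registers the subject and is to "assign a unique an Enrollment ID before initiation of the study drug administration". Under D, "A subject failing to meet all protocol requirements may not be registered". Under G, a consented subject with no tracer "infusion is classified as a screen failure", with no exception for someone already registered; the subject number, demographics and reason are kept. H replaces screen failures, and also anyone who lacks an infusion and its scans.
- **Section 13.5.** "A subject who is enrolled into the study but does not complete the study will be considered prematurely discontinued". The reasons include "Subject is withdrawn due to an AE". Neither statement is conditional on infusion.
- **Section 11.5.1.** Disposition covers everyone who signs consent. "The numbers of subjects screened, enrolled, completed, and discontinued during the study" are summarised by cohort, with reasons for discontinuation after enrollment and a by-subject listing.
- **Section 10.5.** The safety outcomes include "Incidence of withdrawals due to AEs", and "Analyses of safety outcomes will be conducted using the safety population". Section 11.4.3 limits that population to dosed subjects. Section 12.3 starts AE reporting after the first infusion, and note 4 to Tables 1 and 2 treats earlier events as baseline.

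**The concern.** Read literally, the rules give one person two statuses. A subject can be eligible, hold an Enrollment ID, and still leave before the tracer is given. Section 13.5 then counts a discontinuation, and Appendix 2 G counts a screen failure.

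The situation is foreseeable. Section 5 places the IV line, positions the subject and runs the low-dose CT before infusion, and section 7.1.1 names claustrophobia and bruising at the IV site as risks. Such a subject may already have received the study CT, estimated at 10 mSv in section 7.1.2, and would still be labelled a screen failure.

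There also seemed to be a safety consequence: someone who withdrew on the table because of an untoward event would contribute nothing to the listed outcome of withdrawals due to AEs. In cohorts this small, one person visibly moves any percentage, including the feasibility percentage in section 10.6, which has no stated denominator.

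**Working it through.** The plan states no figure to reproduce; section 11.1 says that no power calculation was made. The check is mainly text against text, with a small illustration.

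**Step 1: is the overlap real?** Yes. B puts registration before dosing, 13.5 has no infusion condition, and G has no exception for registered subjects. The one escape is that *enrolled* is never defined. Tables 1 and 2 repeat the eligibility assessment on the scan day, and inclusion criterion 3 requires ability to comply with the procedures. Screening can therefore be read as running up to infusion, with 13.5 applying afterwards. The Enrollment ID in B counts against that reading, so the ambiguity remains.

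**Step 2: what does the label change?** Take one registered, uninfused subject.

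| Item | If screen failure (G) | If discontinued (13.5) |
|---|---|---|
| Safety population (11.4.3, dosed) | out | out |
| Efficacy population (11.4.1, scanned) | out | out |
| Per-protocol population (11.4.2, subset of efficacy) | out | out |
| Replacement (H) | yes | yes |
| Reason recorded | yes (G) | yes (13.5) |
| By-subject disposition listing (11.5.1) | yes | yes |
| Discontinued count in 11.5.1 | 0 | 1 |

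Only the last row differs.

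**Step 3: does the label cause the missing AE withdrawal?** No. The subject is outside 10.5 because the safety population requires a dose and because AE reporting has not begun. Rewriting G would leave both facts in place. Nor must the summary tables disagree about AE withdrawals: that would require the event to be an AE for 13.5, whereas 12.3 and note 4 make it baseline.

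**Step 4: does section 5 contradict 12.3?** It says that the day-7 contact with healthy subjects covers AEs attributable to the scan or to the tracer. That contact follows a completed scan, and the PET acquisition of up to 90 minutes follows infusion, so events during it fall inside the 12.3 window. Only IV placement, positioning and the CT lie outside. The two passages are compatible.

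**Step 5: size under an assumed event.** Assume that one registered subject in a cohort stops before infusion because of an untoward event, is replaced, and that all *n* infused subjects are evaluable. The documents give no rate for this; with no such subject every difference is zero.

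- Withdrawals, dosed denominator: 0/*n* = 0/2 or 0/4 = 0%.
- Withdrawals, registered denominator: 1/(*n* + 1) = 1/3 = 33.3%, or 1/5 = 20.0%.
- Feasibility, infused denominator: *n*/*n* = 2/2 or 4/4 = 100%.
- Feasibility, registered denominator: *n*/(*n* + 1) = 2/3 = 66.7%, or 4/5 = 80.0%.

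The gaps look large only because *n* is 2 to 4. They compare the plan's counting rule with an alternative rule for a supposed event, and do not measure an error in the plan.

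**The case for a change.** The best argument for a change is that it would be cheap and is best made in advance. About one sentence each in Appendix 2 G, 10.5 and 10.6 would give such a subject one category, count the withdrawal over registered subjects, and fix the feasibility denominator. No passage says that enrolled means infused. The event is foreseeable, and settling the category afterwards means settling it with the result known. Calling someone who has had a study CT a screen failure is also not a natural description.

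Part of this stands. The definitional overlap exists, and a colleague tidying the document could reasonably define *enrolled*. The rest is weaker. A registered-subject denominator for AE withdrawals is a preference: it brings in people who leave for unrelated reasons, such as withdrawn consent. It also requires events to be judged as AEs before AE reporting opens, so 12.3 and note 4 of both tables would probably have to change as well, which is more than the few sentences suggested. Deciding afterwards carries little risk when the study is descriptive and a listing shows each person with the reason. The feasibility percentage is not among the objectives in section 3 and drives no decision.

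**Conclusion.** No change follows. The two labels do overlap for a registered subject who stops before the first infusion, and it is fair to call that a loose definition. It is a gap that an analyst fills sensibly: show the person once in the disposition table, state that they were registered but not infused, give the reason, and print the numerator and denominator beside any percentage.

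The effect is at most one entry moved between disposition rows for each such subject. The analysis populations and replacement are the same under either label, and the TEAE rules rest on dosing, which the label does not alter. Excluding uninfused subjects from the safety outcomes is a conventional choice made elsewhere in the plan.

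This rests on three things: the study stays descriptive, with 2 to 4 subjects per cohort (4 to 8 in all) and no test; the by-subject listings of 11.3 and 11.5.1 are produced as planned; and reasons are recorded as G and 13.5 require. The point concerns the first infusion only. A patient who stops before the optional second scan has already been dosed, is in the safety population, and is not a screen failure under G.
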